9.4.2 Efficacy

9.4.2.1 Primary Endpoint(s)

Modules 1 and 2:

The primary endpoint is the progression free survival rate at 6 months, based on investigator

RECIST 1.1 assessments.

Progression free survival rate at 6 months is defined as the proportion of patients who remain alive and free of progression at 6 months.

Module 3:

ORR, defined as the proportion of patients with a best overall response of CR or PR, based on local investigator assessment, as defined in RECIST 1.1.

9.4.2.2 Secondary Endpoint(s)

Objective response rate is defined as the proportion of patients with a best overall response of CR or PR, based on local investigator assessment, as defined in RECIST 1.1. Confirmation of response is required for declaring PR or CR as the BOR. A confirmed response is defined as a CR or PR followed by a CR or PR a least 4 weeks later. The ORR will be summarised with accompanying 90% confidence interval calculated using the Clopper Pearson method. This will be calculated on the full analysis set and the evaluable analysis set. In the summary tables the incidence of unconfirmed responses will be presented as well as the patients with confirmed responses.

Disease control rate (DCR) is defined as the proportion of patients with a best overall response of either CR, PR or stable disease (SD) for at least 6 weeks (corresponding to SD for at least 1 scheduled scan post baseline). A time window of 1 week around the visit will be applied. The DCR and associated 90% confidence interval, calculated using the Clopper Pearson method will be presented. This will be calculated on the full analysis set and the evaluable analysis set.

Progression free survival is defined as the time from first dose of study treatment until the date of disease progression or death (by any cause in the absence of progression), regardless whether the patient withdraws from the assigned study treatment or receives another anticancer prior to progression. Patients who have not progressed or died at the time of analysis will be censored at the time of the latest date of RECIST v1.1 assessment of their last evaluable scan; however, if the patient progresses or dies after 2 or more missed scheduled scanning visits, the patient will be censored at the time of their last evaluable scan prior to the missing scan visits. If the patient has no evaluable visits or does not have baseline data they will be censored at 0 days unless they die due to progression within 2 scan visits of baseline. Progression free survival will be listed by patient and will be presented graphically using Kaplan-Meier plots. Median PFS, together with 3 month, 6 month and 12 months PFS rates will be estimated. The estimate for PFS rate at 6 months is the primary endpoint as detailed in Section 9.4.2.1.

[figure not shown]
Percentage change in tumour size will be derived at each visit by the percentage change from baseline in the sum of diameters of target lesions. The best percentage change in tumour size

will be the patient's value representing the largest decrease (or smallest increase) from baseline in tumour size. Best percentage change in tumour size will be presented in waterfall plots and percentage change in tumour size at each visit will be presented in a spider plot.

Overall survival is defined as the time from first day of study treatment until death due to any cause. Any patient not known to have died at the time of analysis will be censored based on the last recorded date on which the subject was known to be alive. Overall survival will be listed by patient and presented graphically using Kaplan-Meier plots. Median, 6 month and 12 month OS rates will be estimated.

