5.1 Core Inclusion Criteria

Participants are eligible to be included in the study only if all of the following criteria apply:

1. Participant must be ≥ 18 years of age at the time of signing the informed consent.
2. Ability to give written informed consent and capable of understanding the protocol requirements listed in the informed consent form (ICF) and in this protocol. Written informed consent must be obtained prior to performing any protocol-related procedures, including screening evaluations. Participants must be willing and able to comply with the study protocol procedures and restrictions.
3. At least one lesion that is measurable by RECIST 1.1 at baseline (within 6 weeks prior to start of study treatment). The measurable lesion must not be chosen for the mandatory paired biopsies.
4. Mandatory paired biopsies; Patients must have at least one lesion suitable for biopsy at screening (which must not be a target lesion for RECIST 1.1) and be willing to provide mandatory tumour biopsy samples as follows:
 - (i) Baseline* (mandatory and must be performed before study treatment commences, except in exceptional circumstances where biopsy is not technically feasible. All patients without a baseline sample must be approved by Sponsor before starting study treatment as a minimum number of 5 paired biopsies per module are required to achieve the study objectives).
 - (ii) On treatment at C1D15 (+ 7 days). The C1D15 tumour biopsy is also mandatory and should be performed unless the investigator judges that this biopsy is contraindicated (high risk biopsy as defined by ASCO guidelines: Levit et al 2019).
- * Archival biopsy (ideally from the same site that C1D15 biopsy will be taken) that were taken after completion of all prior standard of care treatments will be accepted as a baseline biopsy.
5. Adequate organ and marrow function [Note: for Module 3 the samples must be collected within 10 days prior to the start of study treatment]:

- AST/ALT $\leq 3 \times$ ULN for patients with no Liver Metastasis or AST/ALT $\leq 5 \times$ ULN for patients with Liver Metastasis. [Note: for Module 3, AST/ALT must be $\leq 2.5 \times$ ULN for patients with no Liver Metastasis]
- Total Bilirubin $\leq 1.5 \times$ ULN (with the exception of patients with Gilberts disease [$\leq 3 \times$ ULN])
- Serum Creatinine $\leq 1.5 \times$ ULN
- ANC $\geq 1.5 \times 10^9/L$
- Platelets $> 100 \times 10^9/L$

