### 3.2.1.1 Progression Free Survival

PFS is defined as the time from first dose of study treatment (C0D1) until the date of disease progression or death (by any cause in the absence of progression), regardless of whether the patient withdraws from the assigned study treatment or receives another anticancer treatment prior to progression.

Patients who have not progressed or died at the time of analysis will be censored at the time of the latest date of RECIST 1.1 assessment of their last evaluable scan, however if the patient progresses or dies after 2 or more missed scheduled scanning visits (Progression/Death date - Last available scan date $\geq$ 12 +1 weeks), the patient will be censored at the time of their last evaluable scan prior to the missing scan visits. If the patient has no evaluable visits or does not have baseline data, they will be censored at 0 days. However, if the patient dies within 2 scan visits of first dose (within 12 + 1 weeks from first dose date without a post baseline scan) then its death date will be treated as their progression date. Progression free survival rate at 6 months is the primary endpoint. PFS time is defined as:

$$\text{PFS (days)} = \text{Date of documented PD, Death or last RECIST 1.1 assessment} - \text{first dose of study treatment (C0D1)} + 1$$

Progression free survival rate at 6 months will be defined as the proportion of patients alive and progression free at 6 months.

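### The rules for early deaths without an evaluable scan do not match the any-cause PFS definition or each other, so some deaths can be censored at day 0 and the 6-month PFS rate can be raised

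*Protocol*

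**What the plan says.** **Definition.** Protocol 9.4.2.2 runs PFS from first dose "until the date of disease progression or death (by any cause in the absence of progression". SAP 3.2.1.1 uses the same event: "disease progression or death (by any cause in the absence of progression".

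**Protocol exception.** For a patient with no evaluable visits or no baseline data, Protocol 9.4.2.2 says "they will be censored at 0 days unless they die due to progression within 2 scan visits of baseline". An early death is kept as an event only if progression caused it.

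**SAP exception.** SAP 3.2.1.1 starts from the same default: "If the patient has no evaluable visits or does not have baseline data, they will be censored at 0 days". It then makes an exception for a patient who dies within two scan visits of first dose, spelled out as "within 12 + 1 weeks from first dose date without a post baseline scan"; "then its death date will be treated as their progression date". There is no cause-of-death condition, but there is a condition that no post-baseline scan was done.

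**Use.** The 6-month PFS rate is the primary endpoint of Modules 1 and 2 (Protocol 9.4.2.1). SAP 4.11.2 and 4.11.2.1 estimate it by Kaplan-Meier on the full analysis set, with 90% and 95% confidence intervals.

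**The concern.** An exception to a censoring rule should not narrow the endpoint's own definition of an event, and here both exceptions do. The protocol version excludes early deaths from toxicity, infection or any other non-progression cause. The SAP version excludes early deaths that follow an NE scan, or that occur in a scanned patient without baseline data.

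A patient censored at time 0 leaves the Kaplan-Meier risk set before the first event. A known failure is then treated as no information. In a single-arm module judged against a fixed benchmark, that error can only favour RXC004. The two documents also give different answers for the same patient on the primary endpoint.

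**Working it through.** **Step 1: the plan's own figures.** Protocol 10.9.1 and 11.9.1 state type I and II error rates of 0.06 and 0.10 (Module 1) and 0.06 and 0.20 (Module 2). The sample size, cut-off and both reference rates are redacted, so these cannot be reproduced. The point does not depend on them.

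**Step 2: apply each rule to the same patients.** Day 30 and day 58 both fall within 13 weeks (91 days) of first dose and before the second scheduled scan at week 12.

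| Patient | Any-cause definition | Protocol rule | SAP rule, literal |
|---|---|---|---|
| No scan; toxic death, day 30 | Event | Censored, day 0 | Event |
| No scan; progression death, day 58 | Event | Event | Event |
| Only scan NE (week 6); non-progression death, day 58 | Event | Censored, day 0 | Censored, day 0 |
| Only scan NE (week 6); progression death, day 58 | Event | Event | Censored, day 0 |
| No baseline data, scanned at week 6; non-progression death, day 58 | Event | Censored, day 0 | Censored, day 0 |
| Baseline data and an evaluable week-6 scan; death, day 58 | Event | Event (exception not needed) | Event (exception not needed) |

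NE is an outcome the plan provides for. SAP appendix Table 3 assigns it when not all target lesions are evaluated, non-target disease has not progressed and there is no new lesion. In the fourth row the SAP is stricter than the protocol.

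**Step 3: effect on the estimate.** Let n be the patients in the analysis, k those progression free at 6 months, and d the early deaths censored at day 0. With no other censoring before 6 months:

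- deaths counted as events: rate = k/n
- deaths censored at day 0: rate = k/(n-d)
- ratio = n/(n-d), which is above 1 whenever d is at least 1

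At an assumed 20%: 3/15 = 20.0% becomes 3/14 = 21.4% or 3/13 = 23.1%; 4/20 becomes 4/19 = 21.1% or 4/18 = 22.2%; 6/30 becomes 6/29 = 20.7% or 6/28 = 21.4%.

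**Step 4: other plausible rates.** Protocol 10.3.2 cites a median PFS of 3.1 months in second-line PDAC, and Protocol 11.5.1 cites 4 months in BTC. Under an assumed exponential curve, 6-month PFS is 0.5^(6/3.1) = 26.1% and 0.5^(6/4) = 35.4%. With k rounded to whole patients, Kaplan-Meier at 6 months gives:

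| n (assumed) | k | d = 0 censored | d = 1 | d = 2 |
|---|---|---|---|---|
| 15 | 4 | 26.7% | 28.6% | 30.8% |
| 15 | 5 | 33.3% | 35.7% | 38.5% |
| 20 | 5 | 25.0% | 26.3% | 27.8% |
| 20 | 7 | 35.0% | 36.8% | 38.9% |
| 30 | 8 | 26.7% | 27.6% | 28.6% |
| 40 | 10 | 25.0% | 25.6% | 26.3% |

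In this second set, which spans n = 15 to 40, one death adds about 0.6 to 2.4 points and two add about 1.3 to 5.1 points.

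**Step 5: the stop rule.** Protocol 10.9.1 and 11.9.1 also set a number of patients progression free at 6 months at or below which development is not supported. A patient who died early is not in that number however the record is censored, so the count does not move. The same sections say that the 6-month PFS estimate or rate also guides the decision, and that quantity can move.

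**The case against.** The strongest answer is that the SAP already repairs the main fault. Protocol 9.4 leaves the detailed description of the analyses to the SAP. The SAP drops the cause condition, fixes the clock at first dose and gives an explicit window. A never-scanned patient who dies early from any cause is an event in the planned analysis, and the bias for that group is zero.

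What is left is a small group. The SAP's scan condition may have been meant as shorthand for having no evaluable visit. Missing baseline data should be rare, because entry requires "At least one lesion that is measurable by RECIST 1.1 at baseline (within 6 weeks prior to start of study treatment". The stop-rule count is also unaffected.

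All of this stands as a limit on size, but it does not close the gap. A scan that is NE is still a scan, and a program written to the SAP's words would censor that death at day 0. The protocol still contradicts its own definition and differs from the SAP on the primary endpoint. The readable entries in SAP 4.16 do not mention this difference. One entry there is redacted, so an omission cannot be asserted.

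**Conclusion.** The point holds as a wording fault with a one-directional effect. The protocol's rule contradicts its any-cause definition. The SAP corrects this for unscanned patients and leaves a literal gap for patients with NE-only scans, or with a scan but no baseline data. If d deaths fall in that gap, the Kaplan-Meier 6-month rate is multiplied by about n/(n-d). With one or two deaths, an assumed n of 15 to 40 and no other early censoring, that is roughly 0.6 to 5.1 points. If there are none, the effect is zero.

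A reader might infer more than the documents support:

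- **That the 6-month rate is overstated as planned.** This needs at least one death in the remaining gap, and nothing in the documents says how many to expect.
- **That the protocol window can close as early as week 7 on treatment, because the baseline scan may be 6 weeks old.** That borrows the SAP's 13 weeks. The protocol rule counts scan visits, and Protocol 4.1 schedules these from the start of treatment, so the first two fall at weeks 6 and 12.
- **That the Phase 1 figure of 2/25 adverse events leading to death (Protocol Table 2) measures the frequency.** Those deaths were at 1.5 mg and 3 mg, with none among the 3 + 6 = 9 patients at 1 mg and 2 mg. Neither is shown to have occurred without an evaluable scan.

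**What to change.** Put one rule in Protocol 9.4.2.2 and SAP 3.2.1.1:

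*A patient with no evaluable post-baseline assessment (no scan, or only NE scans) or no baseline data who dies from any cause within 12 + 1 weeks of first dose has a PFS event on the date of death.*

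- **Protocol:** delete *due to progression* and replace *of baseline* with *of first dose*.
- **SAP:** replace *without a post baseline scan* with the condition in the rule above, so that it covers NE-only scans and missing baseline data.
- **SAP 4.16:** list the difference from the protocol, if it is not already there.

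The 12 + 1 week limit stays as it is. The cost is about one sentence in each document and a matching line in the derivation program. The only downside for the sponsor is a 6-month PFS rate that is either unchanged or slightly lower.

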9.4.2.3 Tertiary/Exploratory Endpoint(s)

9.4.3 Safety

9.4.3.1 Adverse Events

Treatment-emergent AEs (TEAEs) are defined as AEs with an onset after dosing and pre-existing AEs that worsen after the start of dosing and within 30 days of stopping RXC004 monotherapy, or 90 days after the last dose of pembrolizumab (for patients in Module 3), or 30 days following cessation of pembrolizumab study treatment if the patient initiates new anticancer therapy, whichever is earlier. For AEs, verbatim terms in the CRF will be mapped to preferred terms and system organ class using the Medical Dictionary for Regulatory activities (version 22.0 or later). CTCAE criteria v5.0 will be used to grade the severity of AEs. The incidence of TEAEs will be summarised by preferred term and system organ class as well as severity. Treatment-related TEAEs will be summarised in the same way. Per-patient incidence of SAEs will also be produced.

By patient, listings of all AEs, deaths, SAEs and TEAEs leading to discontinuation will also be produced.

9.4.3.2 Laboratory Parameters

Shift tables to characterise changes from baseline to on treatment will be presented for haematology, clinical chemistry and coagulation parameters. Laboratory tests with numerical grading criteria in the NCI CTCAE v5.0 will be graded accordingly. Grade 0 will be assigned for all non-missing values not graded as 1 or higher. For laboratory tests where grades are not defined by CTCAE v5.0, results will be classified as low, normal or high based on laboratory normal ranges,

9.4.3.3 Vital Signs

Vital signs data will be presented in listings. Abnormal vital signs values will be identified as those outside (above or below) the reference range. Vital signs data will be summarised using descriptive statistics.

9.4.4 Other Analyses

9.4.4.1 Demographic and Other Baseline Characteristics

Demographic and baseline characteristics will be summarised. For continuous demographic variables, results will be summarised and presented as n, mean, standard deviations, median and minimum and maximum values. For categorical variables the frequency and percentage of patient will be used.

9.4.4.2 Prior and Concomitant Therapy

All investigator terms for medications recorded in the eCRF will be coded to standard names using the World Health Organization Drug Dictionary and further coded to the appropriate Anatomical-Therapeutic-Chemical code.

Prior medications will be defined as medications that stopped before the first dose of study drug and will be summarised and listed.

Concomitant medications will be defined as medications that (1) started before the first dose of study drug and were continuing at the time of the first dose of study drug or (2) started on or after the date of the first dose of study drug. Concomitant medications will be summarised and listed.

9.5 Interim Analyses

There are no formal interim analyses planned.

9.6 Safety Monitoring Committee

An SMC will be appointed to review safety data from patients in this study and a second study of RXC004 in patients with colorectal cancer (RXC004/0002).

The SMC will comprise experts in the disease areas under investigation, who may be study investigators, a biostatistician and an independent bone metabolism expert. The SMC will be convened to review the safety and tolerability of RXC004 at regular intervals.

The safety reviews will start when approximately █ patients across the phase 2 clinical trial program have been dosed for at least 1 cycle of study treatment and will continue every 6 months until the phase 2 studies close or last patient discontinues study treatment (whichever occurs first). A safety review of the combination data will be conducted after █ patients have received the combination of RXC004 and pembrolizumab for at least 1 cycle. Additional safety reviews may be performed at other times as deemed appropriate by the Sponsor or SMC.

As the studies are open label, there are no blinding issues associated with performing interim safety reviews. Full details of the SMC procedures, processes, and analyses can be found in the SMC Charter.

MODULE 1 (PDAC)

10 MODULE 1 (PDAC)

10.1 Background

In 2020, it is estimated that pancreatic cancer will account for 18% of all newly diagnosed cancers in the US (Siegel et al 2020). For metastatic pancreatic cancer, which accounts for approximately 50% of pancreatic cancer diagnoses, the prognosis remains poor with a median OS of 10-12 months with SoC therapy (Thibodeau and Voutsadakis 2018, Von Hoff et al 2011, Conroy et al 2011 and Burris et al 1997). Standard first-line therapies for metastatic pancreatic cancer are FOLFIRINOX (patients with performance status 0-1) or gemcitabine (GEM) combinations, such as GEM plus Nab-paclitaxel (PS 0-2) or GEM plus cisplatin (for patients with BRCA mutations).

There is no standard second-line treatment; therapy option depends on previous treatment and performance status, and include combination or single agent chemotherapies, targeted agents and chemoradiation. Second-line studies have reported PFS of 1.5-3 months and OS of 3-7 months (Wang-Gillam et al 2016, Pelzer et al 2011 and Citterio et al 2018).

10.2 Module 1 Rationale

RXC004 is a small-molecule PORCN inhibitor which reduces Wnt signalling and therefore may offer an opportunity to deliver clinical benefit in tumours that have aberrantly activated Wnt signalling.

RNF43 is an integral membrane E3 ubiquitin ligase that promotes degradation of cell-surface Wnt receptors. Approximately 5-10% of all pancreatic cancers harbour a LoF RNF43 mutation (Waddell et al 2015, Jiang et al 2013, Bailey et al 2016), which leads to increased Wnt receptors at the cell surface and hence hyper-activated Wnt signalling.

Blocking Wnt signalling with PORCN inhibitors has been shown to suppress the growth of RNF43-mutant pancreatic cancers in pre-clinical models (Madan et al 2016, Jiang et al 2013). Furthermore, RXC004 has shown activity in pre-clinical CAPAN 2 xenograft models, which carry a RNF43 LoF mutation.

RXC004 warrants further development in patients with RNF43-mutation positive advanced (unresectable)/metastatic PDAC that has progressed following first-line standard of care treatment.

10.3 Benefit-Risk Assessment

10.3.1 RXC004 Risks

The risk assessment for RXC004 monotherapy treatment can be found in Section 2.3.

10.3.2 Benefit Assessment

This Module will evaluate RXC004 monotherapy in patients with advanced (unresectable)/metastatic pancreatic ductal adenocarcinoma with RNF43 loss of function (RNF43 LoF) who have received 1 prior systemic treatment.

In 2020, it is estimated that pancreatic cancer will account for 18% of all newly diagnosed cancers in the US (Siegel et al 2020). Approved first-line therapies for metastatic pancreatic cancer include FOLFIRINOX (a combination of irinotecan, folinic acid and fluorouracil) in patients with ECOG performance status 0-1 or gemcitabine (GEM) combinations, such as GEM plus Nab-paclitaxel or GEM plus cisplatin (for patients with BRCA mutations) in patients with ECOG 0-2 performance status. In patients with poorer performance status (ECOG 2) gemcitabine monotherapy is commonly used. For metastatic pancreatic cancer, which accounts for approximately 50% of pancreatic cancer diagnoses, the prognosis remains poor with a median OS of 7-12 months, an ORR of 7-32%, and median PFS of 3.7-6.4 months with 1st-line SoC therapy (Von Hoff et al 2011, Conroy et al 2011). Liposomal irinotecan combined with 5-FU/LV is the only approved treatment for 2nd-line metastatic PDAC (Wang-Gillam et al 2016) with ORR, mPFS and mOS of 16%, 3.1 and 6.2 months, respectively. The 6-month PFS rate (%) reported was █%. Second-line treatments have led to PFS of 1.5 to 3 months and OS of 3-7 months (Pelzer et al 2011, Wang-Gillam et al 2016, Citterio et al 2018).

The Phase 1 study of RXC004 enrolled unselected patients with advanced cancers with a median of three prior lines of treatment. Of 18 RECIST-evaluable patients, five had SD, in one case lasting for up to 26 weeks. All five of these patients with SD had Wnt-ligand-dependent tumours, supporting the hypothesis that RXC004 will have clinical activity in selected tumours that are dependent on Wnt ligand signalling pathways (Cook et al 2021).

In the expansion cohort of the WNT 974 study (Rodon et al 2021), stable disease was observed in 10 out of 28 patients, which was enriched in patients with RNF43 mutations.

RXC004 as a single agent therefore has potential to demonstrate clinical benefit in this in this genetically selected advanced (unresectable)/metastatic PDAC population with a large unmet medical need.

